10.4. Outcome related to serious adverse events

Adverse and serious adverse event reporting and categorization

- Vomiting: Persistent vomiting or projectile vomiting in an infant reported by mother, within duration of 6 months (Observed or reported).
- Poor feeding/suck: If an infant develops poor feeding/suck or is unable to feed within duration of 6 months (Observed or reported).
- Necrotizing Enterocolitis: Abdominal distention/tenderness, bowel movements, signs of infection such as apnea (stop breathing), and lethargy within duration of 6 months (Observed or reported).
- Diarrhea: Loose stool in an infant reported by mother, lead to severe dehydration, within duration of 6 months (Observed or reported).
- Respiratory: Respiratory distress: Fast breathing (60 or more breathes per minutes) and/or severe chest in drawing and/or baby turn bluish, within duration of 6 months (Observed or reported).
- Rash: An appearance of itchy, red, painful, and irritated skin, visible by health worker or reported by family, within duration of 6 months (Observed or reported).

Serious Adverse Event

Any adverse event will be labeled as a “Serious Adverse Event” (SAE) if it leads to:

- Intravenous therapy
- Hospitalization
- Life threatening situation
- Death

This is defined per clinician’s assessment

Definition of mortality

Infant Mortality	Any infant death under one year of age. ⁴ An agreement was reached to also capture cause of death ⁵ , date of death, and time of death (if death is within 7 days of birth).
Neonatal mortality	Deaths among live births during the first 28 completed days of life (0-27 days). Rate (per 1000 live births) Numerator: # deaths <28 days Denominator: # live births
Maternal Mortality	Maternal death from any cause related to or aggravated by pregnancy or its management (excluding accidental or incidental causes), during pregnancy and childbirth, or within 42 days of termination of pregnancy.

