8. ADVERSE OUTCOMES

8.1. Afzaaish supplement related – lactating woman only

The trial participants will be instructed/counseled to report any adverse events (minor or major), which may be serious or non-serious in nature. The reporting of the adverse event will take into account any event which may be due to the use of nutritional supplement or with the use of any adjunct therapy, or even death of the trial registered participant (due to any circumstance). *Nutravigilance* is the term used for assessment, understanding, reporting, and prevention of any kind of adverse effects related to the use of food or nutritional supplement. The reporting system for adverse event for dietary and nutritional supplement will follow the Food and Drug Administration (FDA) guidelines so that the information gathered from LW can be used for generating signals/alerts for possible public health concerns and subsequently assessing those signals and taking appropriate safety actions since this nutritional supplement used by LW will ultimately be associated with the health and outcomes of the infants.

Reporting of adverse events on nutritional and dietary supplement includes the range of events from nausea, vomiting, diarrhea, abdominal distension, abdominal pain and rash. LW will be counseled to immediately report any serious condition which appears during the enrollment period, either during follow-up visits by research team or any time through a call on the number provided to them. For this trial the data collected on adverse events and other related reports will be provided by Principal Investigator directly to the DSMB on a monthly basis (serious) in the form of a report, while any fatal adverse events will be reported to DSMB and AKU/VPT IRB within 72 hours of event reported. On every follow-up visit, the research team will collect information for any potential side-effect and health status of LW through active and vigilant surveillance.

Adverse and serious adverse event reporting and categorization

The following **adverse events** will be observed for and documented:

1. Vomiting: The forceful expulsion of gastric contents reported by LW.
2. Diarrhea: Diarrhea is defined as the passage of three or more loose or liquid stools per day (or more frequent passage than is normal for the LW), reported by LW.

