3. Abdominal distention or pain: Conditions/symptoms reported by LW as feeling full, tight, or swollen in the abdomen, i.e. abdomen reported as swollen (distended), hard, and painful, reported by LW.
4. Rash: An appearance of itchy, red, painful, and irritated skin, visible to health worker or reported by LW.

5. Any other serious symptom: If LW has reported any unusual symptoms, which she has never experienced before.

Documentation of adverse event

Adverse event reporting form will be filled against every event which is reported during the course of the study period and in case of any death the routine verbal autopsy form will also be filled. Based on the information provided in the forms, the decision will be made on whether a serious or non-serious adverse event is related to trial intervention.

Serious Adverse Event

Any adverse event will be labeled as a “Serious Adverse Event” (SAE) if it leads to:

- a. Intravenous therapy
- b. Hospitalization
- c. Life threatening situation
- d. Death

Narrative description of serious adverse event will be provided in a document template and attached into the participants file. After reporting of any suspected adverse event, the senior research team/leader, including the study physicians will define the linkages of event with Afzaaish and fill an adverse event reporting form which will define the event in relation to Afzaaish as:

- a) Not related
- b) Unlikely related
- c) Possibly related
- d) Definitely related
- e) Not assessable

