Analysis approach

Statistical analysis will be performed by Stata, version 15. The baseline characteristics will be assessed by arm. The primary analysis will be an intention-to-treat (ITT) analysis. We will compare the mean length velocity (cm/ month) (primary outcome), weight velocity (gm/kg/day), LAZ, WLZ, and WAZ between the two intervention arms and the control arm using ANOVA, with the model adjusted for the birth weight and age of the infants at enrollment. If an outcome is missing for the intention-to-treat infants, the means from that group will be imputed.

Safety outcomes

i. Maternal serious adverse events

The occurrence of maternal SAEs will be expressed as the proportion of women with at least one SAE during the follow-up period (from enrolment to 179th day). The proportion will be calculated by dividing the number of women with at least one recorded SAE by the total number of enrolled participants. Results will be shown both as proportions of participants with any SAE as well as tabulated by the SAE category (death, hospitalization, other). If any participant has experienced more than one type of SAE, the participant will be recorded in each category.

ii. Infant serious adverse events

The occurrence of infant SAEs will be expressed as the proportion of babies with at least one SAE during the follow-up period (from enrolment to 179th day). The proportion will be

calculated by dividing the number of babies with at least one recorded SAE by the total number of recorded newborns. Results will be shown both as proportions of participants with any SAE as well as tabulated by the SAE category (death, hospitalization, other). If any participant has experienced more than one type of SAE, the participant will be recorded in each category.

Interim analysis

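### Non-serious maternal adverse events, including the side effects the protocol names for the supplement, are recorded but have no planned summary by arm

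*SAP*

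**What the plan says.** **Collection.** Protocol 8.1 gives the events expected with the supplement: "Reporting of adverse events on nutritional and dietary supplement includes the range of events from nausea, vomiting, diarrhea, abdominal distension, abdominal pain and rash". Its numbered list then defines them for the lactating woman, for example "Vomiting: The forceful expulsion of gastric contents reported by LW" and "Abdominal distention or pain: Conditions/symptoms reported by LW as feeling full, tight, or swollen in the abdomen", followed by diarrhoea, rash and a residual item for other unusual symptoms. Nausea is in the text but has no numbered definition. Enquiry is active: "On every follow-up visit, the research team will collect information for any potential side-effect and health status of LW". Recording is not limited to serious events: "Adverse event reporting form will be filled against every event which is reported during the course of the study period". Each event is then graded for its relation to Afzaaish.

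**Analysis.** The maternal safety outcome in Protocol section 10 is "the proportion of women with at least one SAE during the follow-up period", tabulated as death, hospitalization or other. Protocol 8.1 sends reports "directly to the DSMB on a monthly basis (serious) in the form of a report", with fatal events reported sooner. SAP 10.4 has a subheading that covers both adverse and serious adverse events, but its symptom list opens with "Vomiting: Persistent vomiting or projectile vomiting in an infant reported by mother, within duration of 6 months" and continues in the same vein. SAP section 12 describes no safety analysis. The maternal adverse-event rows in SAP Table 3 are 'Infant deaths', 'Hospitalization' and 'Injectable therapy'.

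**The concern.** The supplement is the main intervention, and two of the three arms are asked to eat it daily until the infant is six months old. The harms the protocol names in advance are mostly intolerance: stomach and bowel symptoms and rash. Most such events would not be expected to lead to IV treatment, admission, threat to life or death. A safety analysis confined to SAEs is therefore aimed away from the harms the protocol itself expects.

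The protocol presents the trial as evidence for policy on a locally made product and says an ideal product has no side effects. Followed as written, the plan would judge maternal safety on SAEs alone. It would also leave any summary of tolerability to be designed after the results are known, in an open-label trial, where the choice of what to show matters most.

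**Working it through.** The point rests on tracing the recorded data to each planned output. The plan gives no figure to reproduce.

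**Step 1: trace the maternal symptoms to every safety output.**

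| Planned output | What it covers | Non-serious maternal symptoms by arm? |
|---|---|---|
| Protocol 8.1, monthly DSMB report | Serious events | No |
| Protocol 10, safety outcomes | Women, and infants, with at least one SAE, by consequence | No |
| Protocol 10, minimum interim content | SAEs and growth outcomes | No |
| Protocol 10 and SAP 15, harm guideline | SAE incidence | No |
| SAP 10.4, symptom list | Infant symptoms (step 2) | No |
| SAP 10.4, mortality definitions | Infant, neonatal and maternal death | No |
| SAP 12, analysis plan | Growth outcomes | No |
| SAP Table 3, maternal rows | 'Infant deaths', hospitalization, injectable therapy | No |

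**Step 2: whose symptoms are listed in SAP 10.4?** Set beside the two protocol lists:

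- Vomiting, poor feeding, necrotizing enterocolitis, diarrhoea, respiratory distress and rash are the six items of Protocol 8.2 (azithromycin, infants), in the same order. The 24-hour window after the dose has become six months.
- Vomiting, feeding and diarrhoea name the infant; the respiratory item names the baby.
- Rash names no subject. Its reporter is the family, as in Protocol 8.2. The maternal rash item in Protocol 8.1 is reported by the woman herself.
- Abdominal distension appears only within necrotizing enterocolitis. The maternal definitions of vomiting, diarrhoea and abdominal symptoms are absent.

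The SAP has thus carried over the infant list and left out the maternal one. The 'Infant deaths' row in the maternal block of Table 3 suggests that the infant rows were copied there too.

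**Step 3: what happens to a serious maternal event?** A woman admitted with diarrhoea is counted in the Protocol 10 SAE proportion and in the hospitalization row of Table 3. She is shown under the consequence; no planned table says the cause was diarrhoea.

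**Step 4: was Arm A asked the same questions?** Protocol 8.1 speaks of trial participants in general and of every follow-up visit, which points to all arms. But its heading is specific to the supplement, and its grading is relatedness to Afzaaish. The visit schedule in Protocol 6.12 lists compliance, newborn danger signs, child illness history and breastfeeding recall, with no maternal symptom item. The table in Protocol 7.3 lists vital status for all arms and no maternal symptom enquiry. Equal ascertainment is likely but not shown.

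**Step 5: possible size.** Women assigned the supplement: 2 × 319 = 638 of 957. The risks below are assumptions chosen to show a range.

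Excess women = 638 × (p₁ − p₀). The 95% half-width for B+C versus A = 1.96 × √[p₀(1 − p₀)/319 + p₁(1 − p₁)/638].

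| Assumed risk, A vs B+C | Excess women | 95% half-width |
|---|---|---|
| 2% vs 5% | 638 × 0.03 = 19 | 1.96 × √(0.0000614 + 0.0000745) = 2.3 points |
| 5% vs 10% | 638 × 0.05 = 32 | 1.96 × √(0.0001489 + 0.0001411) = 3.3 points |
| 10% vs 20% | 638 × 0.10 = 64 | 1.96 × √(0.0002821 + 0.0002508) = 4.5 points |

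In each case the half-width is smaller than the assumed difference, so a by-arm table would be informative if ascertainment was equal.

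**The case against.** A reader might infer that the supplement's side effects would go wholly unreported. The documents do not support that. Events meeting an SAE criterion are counted in Protocol 10, partly shown in Table 3 and reported to the DSMB. Non-serious events also have a use in the protocol: each gets a form and a relatedness decision, and the data are meant to generate safety signals. The DSMB may ask for analyses beyond the stated minimum. SAP safety reporting is not purely about infants either, since maternal mortality is defined and Table 3 has a maternal block. All of this stands, and it limits the point to non-serious events and to the missing summary by arm.

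It can also be said that Table 3 is a sample shell and has no symptom rows for infants either, so a missing row proves little alone. That is fair. The weight lies on the SAP 10.4 list and Protocol 10, which define what is to be analysed, and neither covers these events.

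A second tempting step is to take the comparison with control as ready to run from completed forms. For Arm A this is not established (step 4). With unequal questioning, a difference between B+C and A would partly measure how often women were asked.

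Finally, a power statement would rest on assumed rates and would depend on the test chosen. A descriptive harms table does not need one.

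**Conclusion.** The point holds for non-serious maternal adverse events. Protocol 8.1 names, defines (nausea apart) and records them, and no section of either document plans a summary by arm. Serious maternal events are covered, by consequence and not by symptom. As the plan stands, conclusions on maternal safety in the 638 women assigned the supplement would rest on SAEs alone.

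The number of women concerned is unknown. The range of about 19 to 64 excess cases depends wholly on assumed excess risks of 3 to 10 percentage points and includes any cases that became serious. The gap itself does not depend on those figures. Whether it can be closed with a comparison against control depends on Arm A having had the same questions at the same visits. The primary efficacy analysis is unaffected. The change should be made before the treatment code is revealed.

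**What to change.** 1. In SAP 10.4, add the maternal events of Protocol 8.1 with their definitions, beside the infant list. Include nausea, which needs a definition, and the residual item for other symptoms. State whose rash the existing item means.
2. In SAP Table 3, add for each event type the number and percentage of women with at least one event from enrolment to day 179, with all women randomised to the arm as denominator. Give the risk difference with 95% confidence interval for B vs A, C vs A and B+C vs A (both arms receive the same supplement).
3. Before making those comparisons, confirm from the visit forms that Arm A was asked the same maternal symptom questions at the same visits. If it was not, present B and C descriptively, without a comparison to A, and say why.
4. Report the relatedness grades descriptively within B and C only; relatedness to Afzaaish has no meaningful comparator in an arm that does not receive it.
5. Correct the 'Infant deaths' label in the maternal block of Table 3.
6. Make no power claim for these events.

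The cost is SAP wording, one additional table block and a check of the Arm A forms. The downside is that these are self-reports in an open-label trial, so events may be over-reported in B and C; the report must say so.

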1.1.2. Effect of antibiotic prophylaxis for infant

Furthermore, there is also strong debate on the prophylactic use of antibiotics (especially the use of Azithromycin AZM) in averting the risk of stunting and underweight, although there is little evidence in support. The recent studies showed significant impact on the reduction of all causes of under-five mortality, but were unable to demonstrate a statistically significant difference in stunting, underweight, and low MUAC of children. The role of antibiotics on child growth and nutrition remains unclear, but the authors suggested larger studies and longitudinal trials may help determine any association. (9-12) The use and safety profile of AZM in infants is also well documented. A systematic review showed that AZM is the most common antibiotic used to treat several pediatric infections, including bronchopulmonary dysplasia (BPD). (22) Some side effects noted with its use include diarrhea, abdominal pain and vomiting. There is a potential side effect of infantile hypertrophic pyloric stenosis (HIPS). According to one author, the risk is high in the neonatal age and still needs to be further investigated. (23) Its use beyond the neonatal age is considered to be safe. (22, 23)

Justification for using Azithromycin

Literature has provided compelling evidence that AZM is safe for use in young infants and children (10, 23). Use of oral AZM on a mass level to control overall mortality in children living in rural regions has been found efficacious against respiratory diseases, diarrhea and malaria. (11, 12). In another study, giving a single oral prophylactic dose of AZM dramatically reduced the prevalence of infections in endemic areas.

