6.12. Follow ups

There will be specific assessment teams involved in this trial who will conduct their specific follow ups as per the below mentioned schedule to assess the newborn periodically and also measure the compliance of Afzaaish (Arm B and C) also providing routine counseling to all participants (all arms). Furthermore, the follow-up team will comprise of research staff that will be responsible for monthly 24 hour food recall checks. Additionally, they will also be responsible for assessing exclusive breastfeeding status, i.e. exclusive, predominant or partially, in all arms. 24 hours exclusive breastfeeding recall related data will be collected on the visit days. Child illness related history, care seeking, hospitalization and medication related history will be recorded at each visit. These follow up teams will also be in charge of household health promotion and education counseling for all the arms following the already established standard care counseling procedures. Exclusive breastfeeding will be assiduously promoted and precautionary counseling will be done regarding risks associated with giving the infant solids or liquids other than breast milk.

Also an outcome assessment team (Anthropometry team) will be responsible to follow babies on a monthly basis until the age of 6 months to perform anthropometry on both LW and infants. Schedule for follow-ups are as follows:

Activity	Follow-up days, according to the age of the child after enrollment		
1. Afzaaish Compliance, newborn assessment (WHO algorithm of danger sign), past illness history, hospitalization related history, other care seeking, medication related history, 24 hour EBF recall, Afzaaish compliance -44 days are meant for pre and post Azithromycin dose)	1. 1	18. 23	35. 95
	2. 2	19. 25	36. 102
	3. 3	20. 29	37. 109
	4. 4	21. 32	38. 116
	5. 5	22. 35	39. 123
	6. 6	23. 38	40. 130
	7. 7	24. 41	41. 137
	8. 8	25. 42	42. 144
	9. 9	26. 43	43. 151
	10. 10	27. 44	44. 158
	11. 11	28. 48	45. 165
	12. 12	29. 52	46. 172
	13. 13	30. 59	47. 179
	14. 15	31. 67	
	15. 17	32. 74	
	16. 19	33. 81	
	17. 21	34. 88	
2. 24 hours food recall	1. 7		
	2. 35		
	3. 67		
	4. 95		
	5. 123		
	6. 151		
3. Anthropometry and vaccination record	4. 27		
	5. 56		
	6. 85		
	7. 114		
	8. 143		
	9. 177		

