8.2. Azithromycin related – Infant only

To establish safety profile for AZM prophylaxis dose, the infant will be monitored for the next 48 hours. After administration, data will be collected and any side-effects (observed or reported) will be noted by the research team. They will revisit the infants after 24 hours (i.e. after dose, two consecutive visits will be performed with a 24 hour gap). For this trial the data collected on adverse events and other related reports will be provided by Principal Investigator directly to the DSMB on a monthly basis (serious) in the form of report, while any fatal adverse events will be reported to DSMB and AKU/VPT IRB within 72 hours of event reported.

Adverse event reporting form will be filled against every event which is reported over the course of study period and in case of any death the routine verbal autopsy form will also be filled. Based on the information provided in the forms, decision will be made on whether to classify the event as serious or non-serious and also if it was related to trial intervention or not. Post-dose (43 and 44 day) visits will be performed to monitor and observe any suspected adverse event in the infants which are most likely to appear after AZM administration. If in any case, the dose is delayed, the 2 consecutive visits days will be changed accordingly.

Adverse and serious adverse event reporting and categorization

Based on the literature (30), following potential adverse event in infants related to AZM will be monitored:

- i. Gastrointestinal:
 - a. Vomiting: Persistent vomiting or projectile vomiting in an infant reported by mother, within 24 hours of dose administration (Observed or reported).
 - b. Poor feeding/suck: If an infant develops poor feeding/suck or is unable to feed within 24 hours of dose administration (Observed or reported).
 - c. Necrotizing Enterocolitis: Abdominal distention/tenderness, bowel movements, signs of infection such as apnea (stop breathing), and lethargy within 24 hours of dose administration in an infant (Observed or reported).
 - d. Diarrhea: Loose stool in an infant reported by mother, lead to severe dehydration, within 24 hours of dose administration (Observed or reported).
- ii. Respiratory:
 - a. Respiratory distress: Fast breathing (60 or more breathes per minutes) and/or severe chest in drawing and/or baby turn bluish, within 24 hours of dose administration (Observed or reported).

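### The infant diarrhea event requires severe dehydration, and no planned table reports ordinary infant diarrhea by arm, although the protocol names diarrhea as an azithromycin side effect

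*SAP*

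**What the plan says.** Both documents put severe dehydration inside the definition of the infant event.

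- SAP section 10.4: "Diarrhea: Loose stool in an infant reported by mother, lead to severe dehydration, within duration of 6 months (Observed or reported".
- Protocol section 8.2: "Diarrhea: Loose stool in an infant reported by mother, lead to severe dehydration, within 24 hours of dose administration".

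Elsewhere the protocol treats diarrhea differently. Its section on antibiotic prophylaxis for infants says of azithromycin: "Some side effects noted with its use include diarrhea, abdominal pain and vomiting". For mothers, Protocol section 8.1 states: "Diarrhea is defined as the passage of three or more loose or liquid stools per day". In both documents an event becomes serious through a separate list: intravenous therapy, hospitalization, threat to life, or death.

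Three provisions allow milder infant events to be recorded. Protocol section 8.2 says "After administration, data will be collected and any side-effects (observed or reported) will be noted by the research team" and "Adverse event reporting form will be filled against every event which is reported over the course of study period". Protocol section 6.12 adds: "Child illness related history, care seeking, hospitalization and medication related history will be recorded at each visit".

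On reporting, the infant safety outcome in Protocol section 10 is the share of infants with one or more SAEs, split into death, hospitalization and other. The adverse event rows of SAP Table 3 are infant deaths, hospitalization and injectable therapy.

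**The concern.** Protocol section 8.2 sets up post-dose monitoring in order to describe the safety of the azithromycin dose. Diarrhea is the first side effect that the protocol names for the drug, and it is named without a threshold. The defined infant event covers only the episodes that progress to severe dehydration. Seriousness is already judged in a later step, so the clause is a second severity filter placed before the first.

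Under the intervention table in Protocol section 6.4, arms B and C differ only in the infant dose of azithromycin. Arm C against arm A mixes the drug with the supplement. C against B is thus the comparison that could inform a reader about tolerability in infants, and as planned it yields no figure for ordinary diarrhea.

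**Working it through.** **Step 1: the definitions side by side.**

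| Item | Condition in the definition | Window |
|---|---|---|
| Infant diarrhea, Protocol 8.2 | loose stool with severe dehydration | 24 hours after the dose |
| Infant diarrhea, SAP 10.4 | loose stool with severe dehydration | 6 months |
| Maternal diarrhea, Protocol 8.1 | stool count (or more frequent than usual) | none stated |
| Infant rash and poor feeding, both documents | no severity threshold | 24 hours / 6 months |

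The wording of the infant line is loose, but a required condition is its natural reading. It stands in both documents, so it is not a slip in one of them. Rash and poor feeding show that the infant list is not confined to severe events.

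**Step 2: from record to table.** An infant with uncomplicated diarrhea can appear in the post-dose notes, on an adverse event form, or in the illness history. That infant does not meet the defined event. Without one of the four SAE criteria, the infant does not enter the SAE proportion in Protocol section 10 either. No adverse event row in SAP Table 3 would hold the episode. Interim harm review (Protocol section 10, SAP section 15) also looks at SAE incidence. No planned output therefore shows ordinary infant diarrhea by arm.

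**Step 3: illustration of what the clause removes.** The documents give no infant diarrhea rate and plan no test of this item, so the rates and the severe share are assumptions. Only the 319 per arm comes from the plan, and dropout is ignored.

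Expected count = 319 × rate × share with severe dehydration. For example, 319 × 0.20 × 0.05 = 3.19. Power is the sum of the binomial probabilities of all pairs of counts for which Fisher's exact test gives two-sided p ≤ 0.05.

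| Any diarrhea, B v C (assumed) | Episodes counted | Expected infants, B v C | Exact power |
|---|---|---|---|
| 5% v 10% | all | 16.0 v 31.9 | 62% |
| 5% v 10% | 5% severe | 0.80 v 1.60 | 0.3% |
| 5% v 10% | 1% severe | 0.16 v 0.32 | 0.0001% |
| 10% v 20% | all | 31.9 v 63.8 | 93% |
| 10% v 20% | 5% severe | 1.60 v 3.19 | 2.7% |
| 10% v 20% | 1% severe | 0.32 v 0.64 | 0.004% |

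An exact method is needed at these counts. With 319 per arm, 5 v 0 gives p = 0.062, so at least 6 v 0 is required to pass 0.05. A normal approximation gives 4–11% in the reduced rows, which overstates the power.

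**The case against.** The strongest reply is that ordinary diarrhea is not lost. Protocol section 8.2 has any side effect noted, a form filled for every reported event, and each event then classified as serious or not and as related or not. Section 6.12 takes an illness history at each visit. This stands. A reader might infer from the definition that the trial cannot detect ordinary diarrhea at all; the documents do not support that.

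A reader might also infer that the trial will publish a near-zero diarrhea count and so suggest tolerability. This does not follow either, because no diarrhea row is planned. It does mean that changing the definition alone would alter no planned output; the missing tabulation is half of the problem.

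It can further be said that SAP section 10.4 is headed as concerning serious events, and that its vomiting, enterocolitis and respiratory items are also weighted towards severe illness. That is partly right. But the sub-heading covers adverse as well as serious adverse events, rash and poor feeding carry no threshold, and seriousness has its own criteria below the list.

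Finally, removing the clause would not by itself isolate a drug effect. Over 6 months, most of the period lies before or well after a single dose at 42 days. This stands, and the windows have to be part of the fix.

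**Conclusion.** The point holds as a gap in outcome definition and tabulation. The infant diarrhea event in both documents excludes the uncomplicated form of a side effect that the protocol itself names, and no planned table reports that form by arm. It is not a claim that such episodes go unrecorded. The primary efficacy result is unaffected.

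The conclusion rests on the text and not on any rate. The size is an illustration only: on an assumed 10% v 20%, exact power is about 93% for any diarrhea and under 3% if 1–5% of episodes reach severe dehydration; on 5% v 10%, about 62% and at most 0.3%. The change should be made, because it is specific and cheap and serves a safety purpose that the protocol states.

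**What to change.** 1. In Protocol section 8.2 and SAP section 10.4, remove the dehydration clause from the outcome definition of infant diarrhea. The stool-count approach of Protocol section 8.1, read against the infant's usual pattern, is a ready model. Record dehydration as a severity grade and leave seriousness to the existing SAE criteria.
2. Reconcile the 24-hour window in the protocol with the 6-month window in the SAP.
3. Add rows to SAP Table 3, by arm, for any infant diarrhea and for diarrhea with severe dehydration. Show events after the day-42 time point separately from the whole 6 months, using the same age window in all arms. Protocol section 9 allows 7 days around the dose, so the age window should be set with that in mind.
4. Confirm that arms A and B are visited on days 42–44 as arm C is. The schedule in Protocol section 6.12 does not restrict those days by arm, but it links them to the dose.

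The cost is one definition line in each document and a few table rows; the visits and the illness history already exist. There are two downsides. More non-serious events must be tabulated. The events are also mother-reported in an open-label trial, so knowledge of the arm could influence reporting, and the table should carry that caution.
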